### 10.4 Sample Size

The power of the study can be characterized as follows: if the overall absorption rate (defined as the proportion of women with detectable levels of PMPA in plasma, endometrium, cord blood, placental tissue, and/or amniotic fluid) was expected to be 33%, 16 women would provide 72% power to exclude absorption rate > 60%. In addition, the lower and upper bounds of the exact 95% confidence interval (CI) around the absorption rate are 13% and 57%, respectively, if the observed number of absorption in a cohort of 16 women was 5 (31%: 5 out 16).

For endpoints where no or very low absorption rates are expected (e.g., endometrium, cord blood, placental tissue, and amniotic fluid), 16 women would provide 80% power to exclude absorption rate > 25% assuming the true rate of absorption is 5%. In addition, the upper bounds of the exact 95% confidence interval (CI) around the absorption rate are 20% and 30% if the observed number of absorption in a cohort of 16 women was 0 or 1, respectively.

Additional participants may enroll in the study, at the discretion of the protocol team, to replace currently enrolled participants who receive study gel but whose time of cesarean delivery is greater than 8 hours following the time of study gel administration. Thus, in the event that participants are replaced for this purpose, the total sample size at the end of the study may slightly exceed 16 participants who received study gel.

A sample size of 16 women is insufficient to provide a formal statistical assessment for the comparison between the plasma absorption level observed in HPTN 050 and the one that will be observed in this study.

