### **10.6.2 Primary Analysis**

Descriptive statistics to assess women characteristics will be used: for categorical variables, the number and percent in each category; for continuous variables, the mean, median, standard deviation, quartiles and range (minimum, maximum). Similarly, descriptive statistics for continuous variables will be use to describe levels of tenofovir in levels in plasma, in endometrium, in cord blood, in placental tissue, and in amniotic fluid. If a substantial number of women are below the limit of detection of the assay, descriptive statistics for continuous variables will not be used. Rather, proportion of women with detectable levels will be computed along with an exact 95% confidence interval based on the Clopper-Pearson method.

Blood plasma pharmacokinetics of tenofovir will be evaluated after vaginal administration. Pharmacokinetic parameter estimates will include peak concentration ( $C_{max}$ ), time to peak concentration ( $T_{max}$ ), and area under the concentration time curve (AUC) for tenofovir in the blood. Descriptive statistics will be used to summarize these PK parameters in the cohort. Cord blood, amniotic fluid, placental tissue, and endometrial tissue tenofovir levels will also be summarized using descriptive statistics. The ratio of concentrations of tenofovir in maternal blood relative to temporally matched cord blood, amniotic fluid, and endometrial tissue concentrations, and ratio of maternal blood plasma relative to intracellular peripheral blood mononuclear cell (PBMC) tenofovir and tenofovir diphosphate levels will be calculated and summarized using descriptive statistics.

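### The stated 72% power to exclude an absorption rate above 60% is 56% under the exact interval the protocol plans to use

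*Protocol*

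**What the plan says.** Section 10.4 (Sample Size) defines an overall absorption rate: the proportion of women with detectable drug in plasma or in any of the sampled tissues and fluids. It introduces its claim with "The power of the study can be characterized as follows", supposes that this rate "was expected to be 33" percent, and concludes that "16 women would provide 72% power to exclude absorption rate > 60" percent. It names no test, significance level or sidedness for that figure. The next sentence describes precision for 5 detections among 16 women: "the lower and upper bounds of the exact 95% confidence interval (CI) around the absorption rate are 13% and 57%, respectively".

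Section 10.6.2 (Primary Analysis) fixes how such a proportion will be analysed. "If a substantial number of women are below the limit of detection of the assay, descriptive statistics for continuous variables will not be used"; in that case the "proportion of women with detectable levels will be computed along with an exact 95% confidence interval based on the Clopper-Pearson method".

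**The concern.** A power to exclude a rate has meaning only relative to the rule that does the excluding. The only rule the protocol provides is the upper limit of an exact 95% interval. With 16 women the count takes few values, so power moves in large steps from one cut-off to the next, and a normal approximation can land between steps that the exact analysis cannot reach.

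This is the only power statement for the overall absorption rate, which includes plasma and is the quantity closest to study hypothesis 1 in section 10.3. An ethics board or the monitoring committee reading 72% would think that a true rate of 33% leads to exclusion of 60% nearly three times in four. If the real figure is nearer one in two, they are misinformed about what 16 pregnant women can show.

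**Working it through.** **Inputs.** From section 10.4: n = 16, true rate 0.33, rate to exclude 0.60, stated power 72%. From section 10.6.2: exact two-sided 95% Clopper-Pearson interval, so 2.5% in the upper tail. At a 33% rate about two thirds of women would be below the limit, so the condition in section 10.6.2 for using the interval is met.

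**Reproducing the 72%.** Use a one-sample normal approximation, one-sided 5%, no continuity correction, with the null variance for the critical value and the alternative variance for power:

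- standard error at 0.60: √(0.60 × 0.40 / 16) = 0.12247
- standard error at 0.33: √(0.33 × 0.67 / 16) = 0.11755
- z = (0.60 − 0.33 − 1.645 × 0.12247) / 0.11755 = 0.06853 / 0.11755 = 0.583
- Φ(0.583) = 0.720

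So the stated figure is this approximation. With 1.96 in place of 1.645, which matches the upper limit of a two-sided 95% interval, the same formula gives z = 0.02995 / 0.11755 = 0.255 and power of 60%.

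**Power under the planned interval.** The Clopper-Pearson upper limit for x of 16 is the 0.975 quantile of Beta(x + 1, 16 − x). Power for the rule "x or fewer" is P(X ≤ x) with X binomial(16, 0.33).

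| Detections x | Two-sided 95% upper limit | Excludes 60%? | P(X ≤ x), rate 0.33 | P(X ≤ x), rate 0.60 |
|---|---|---|---|---|
| 4 | 52.4% | yes | 0.350 | 0.005 |
| 5 | 58.7% | yes | 0.558 | 0.019 |
| 6 | 64.6% | no | 0.747 | 0.058 |
| 7 | 70.1% | no | 0.880 | 0.142 |

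The largest count that excludes 60% is 5, so power is 55.8%. The shortfall is 72.0 − 55.8 = 16.2 percentage points. With a true rate of exactly one third the power is 54.7%.

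**Does another exact rule give 72%?**

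- No cut-off in the table has 72% power. The nearest is 6 or fewer, at 74.7%.
- That rule is not available even at one-sided 5%: P(X ≤ 6) at a rate of 0.60 is 0.058, and the exact one-sided 95% upper limit for 6/16 is 60.9%. Power at one-sided 5% is therefore also 55.8%.
- The bounds printed in section 10.4 for 5/16 are not Clopper-Pearson, which gives 11.0% to 58.7%. They match a Blaker-type exact interval (13.2% to 56.6%). Its upper limit for 6/16 is 63.2%, so the cut-off stays at 5 and the power at 55.8%.

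**The case against.** The strongest reply is that 72% is not a miscalculation. It is a correct one-sided 5% normal-approximation power, section 10.4 never says it was computed from the exact interval, and the interval arrives in a separate sentence. That is right as an account of where the figure came from. But no such test is stated anywhere in the protocol, and an exact test at the same one-sided 5% level does not have that power either.

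A second reply is that the Clopper-Pearson interval is conditional on a substantial number of women being below the limit, and that sections 2.10 and 7.9.2 expect a more sensitive assay. This would matter if detection turned out to be common. In the scenario for which the power is quoted, it does not: a 33% detection rate triggers the condition.

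Third, the study is a descriptive, single-arm Phase I trial. Excluding 60% drives no stopping rule or success criterion, and the absorption rate is a composite rather than the listed pharmacokinetic endpoints (AUC and Cmax). This stands, and it limits the consequence: the statement needs correcting, while the sample size need not change.

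Finally, the 33% input can itself be questioned, since section 2.10 reports detectable levels in 14 of 25 women (56%) in the earlier study. That is a separate matter. The calculation here takes 33% as given.

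**Conclusion.** The concern holds. Under the exact two-sided 95% interval, 16 women give 56% power, not 72%, to exclude an absorption rate above 60% when the true rate is 33%. The chance of failing to exclude 60% is 44%, against the 28% implied. The fault is a mismatch between the approximation behind the power figure and the planned interval, in both method and error level.

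The result assumes n = 16 evaluable women and a true rate of 33%. It is the same for the Clopper-Pearson interval, for the Blaker-type interval that matches the printed bounds, and for a one-sided exact 5% test.

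**What to change.** Restate the sentence in section 10.4, for example: *If the true rate is 33%, 16 women give 56% power to exclude a rate above 60%, and 75% power to exclude a rate above 65% (exact two-sided 95% Clopper-Pearson interval).* The second clause is optional. It is correct, because 6/16 has an upper limit of 64.6% and P(X ≤ 6) = 0.747, but 65% is a margin the protocol does not otherwise use.

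Once the sentence names Clopper-Pearson, the bounds beside it for 5/16 should be put on the same basis (11.0% to 58.7%), or the paragraph will mix two intervals.

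The cost is an edit to one paragraph and a less favourable stated power. Sample size, procedures and analysis stay as they are. If the team wants about 72% power against 60%, the exact interval first gives it at 22 women (8 or fewer detections, 71.9%); that would be a design decision, not part of this correction.

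### The exact 95% limits in Protocol section 10.4 (13% to 57% for 5/16; 20% for 0/16) are not those of the Clopper-Pearson method that section 10.6.2 names for the analysis

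*Protocol*

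**What the plan says.** Protocol section 10.4 (Sample Size) defines the absorption rate as the proportion of women with detectable drug in plasma or in any of the other sampled fluids and tissues. It then illustrates the precision from 16 women. It states that "the lower and upper bounds of the exact 95% confidence interval (CI) around the absorption rate are 13% and 57%, respectively", and the case is "if the observed number of absorption in a cohort of 16 women was 5 (31%: 5 out 16"). For the endpoints where little or no absorption is expected, it gives upper limits of 20% when no woman shows absorption and 30% when one does. All these limits are called exact, and section 10.4 names no method.

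Protocol section 10.6.2 (Primary Analysis) does name one. If many women fall below the assay's limit of detection, the continuous summaries are dropped and the "proportion of women with detectable levels will be computed along with an exact 95% confidence interval based on the Clopper-Pearson method". No other exact method is named anywhere in the protocol.

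**The concern.** A reader who applies the method of section 10.6.2 to the counts in section 10.4 does not get the limits printed there. The interval at issue illustrates roughly the expected result, since the hypothesised plasma detection rate is about 33% (section 10.3). Section 2.10 expects measurable concentrations in only some women, so the proportion with its interval may well become a main reported statistic. If 5/16 were observed, the report would show a wider interval than the protocol promised for the same data. The upper limit would also lie closer to the 60% rate that section 10.4 sets out to exclude.

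**Working it through.** **Inputs.** n = 16; x = 5, 0 and 1; 95% two-sided (section 10.4). Method for the analysis: Clopper-Pearson (section 10.6.2).

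**Step 1: Clopper-Pearson.** The lower limit is the 2.5% quantile of Beta(x, n − x + 1). The upper limit is the 97.5% quantile of Beta(x + 1, n − x).

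- 5/16, lower: Beta(5, 12) at 0.025 = 0.1102. Check: at p = 0.1102, P(X ≥ 5) = 0.025.
- 5/16, upper: Beta(6, 11) at 0.975 = 0.5866. Check: at p = 0.5866, P(X ≤ 5) = 0.025.
- 0/16, upper: 1 − 0.025^(1/16) = 0.2059.
- 1/16, upper: Beta(2, 15) at 0.975 = 0.3023.

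At the printed limits the tails are not 0.025: P(X ≥ 5) = 0.047 at p = 0.13, and P(X ≤ 5) = 0.034 at p = 0.57. So 13% and 57% are not Clopper-Pearson limits.

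**Step 2: can the printed figures be reproduced?** Several common intervals for 5/16 fail:

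- Wald: 8.5% to 54.0%
- Wilson: 14.2% to 55.6%
- Agresti-Coull: 13.9% to 55.9%
- Jeffreys: 13.1% to 55.6%
- mid-P: 12.5% to 56.3%
- 90% Clopper-Pearson: 13.2% to 54.8%

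None of these is an exact 95% interval. Shorter exact 95% methods do reproduce the figures. Blaker's method keeps a value p when the smaller tail at x, plus the largest opposite tail not exceeding it, is above 0.05.

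- At the lower end for 5/16, the smallest opposite tail is P(X = 0), about 0.10, which is too large to be added. The limit is therefore where P(X ≥ 5) = 0.05, which is p = 0.132.
- At the upper end for 5/16, p = 0.566. There P(X ≤ 5) = 0.037, and P(X ≥ 13), also about 0.037, stops qualifying as the opposite tail.

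| Case | Section 10.4 | Clopper-Pearson | Blaker | Blyth-Still-Casella |
|---|---|---|---|---|
| 5/16, lower | 13% | 11.0% | 13.2% | 13.2% |
| 5/16, upper | 57% | 58.7% | 56.6% | 57.1% |
| 0/16, upper | 20% | 20.6% | 20.1% | 19.7% |
| 1/16, upper | 30% | 30.2% | 30.0% | 29.9% |

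The Blyth-Still-Casella column was obtained numerically, by refining the Clopper-Pearson limits with the largest lower limits moved first; the reverse order does not reproduce the figures. For both shorter methods the minimum coverage at n = 16 over a grid of p is 95.0%, so both are valid exact intervals. Each rounds to all four printed figures. Clopper-Pearson rounds to only one of them, the 30%.

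**Step 3: size.** Width as printed: 57 − 13 = 44 points. Clopper-Pearson width: 58.66 − 11.02 = 47.6 points. Against Clopper-Pearson, the printed lower limit is 2.0 points too high and the printed upper limit 1.7 points too low (58.7 − 57).

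**Step 4: does it change what 16 women can exclude?** Under Clopper-Pearson the upper limit is 58.7% for 5/16 and 64.6% for 6/16. Under Blaker it is 56.6% and 63.2%. Five is therefore the largest count that excludes 60% under either method. For 25%, the largest count is 0 under either method (20.6% or 20.1% for 0/16; 30.2% or 30.0% for 1/16).

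**The case against.** A reader might infer that the 13% to 57% interval is simply miscalculated, and that 20.6% was rounded down to 20%. The document does not support either inference. Section 10.4 says only that the interval is exact, and Clopper-Pearson is one exact method among several. All four printed limits match Blaker's interval, which points to one shorter exact method used throughout the section. On that reading, 20% for 0/16 is ordinary rounding of 20.1%.

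It can also be said that little depends on the difference. Section 10.4 is illustrative, the analysis is descriptive, and the protocol itself says that 16 women are too few for a formal comparison with HPTN 050. The Clopper-Pearson interval in section 10.6.2 applies only if a substantial number of women fall below the limit of detection.

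Both arguments limit the size of the point, but they do not remove it. If a shorter method was used, the protocol plans with one exact method and reports with another, and tells the reader only about the second. If it was not used, the limits are miscalculated. On either account, the named method applied to the stated count does not give the stated interval.

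**Conclusion.** The point stands as an inconsistency between sections 10.4 and 10.6.2, of minor size. For 5/16 the planning statement overstates precision by about 3.6 points of width (47.6 − 44), and the upper limit for 0/16 becomes 21% instead of 20%. The figure for 1/16 is unaffected. The sample size does not depend on the difference, and 5/16 still excludes 60%. The margin falls from 3 points (60 − 57) to 1.3 points (60 − 58.7).

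The conclusion assumes that the Clopper-Pearson commitment in section 10.6.2 covers the absorption rate of section 10.4. Both are described as proportions of women with detectable levels. That the authors used Blaker's or a similar method is inferred from the match of the figures; the document does not say so.

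**What to change.** Either of two changes is enough.

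1. In section 10.4, give the Clopper-Pearson limits: 11% and 59% for 5/16, and upper limits of 21% and 30% for 0/16 and 1/16. Three numbers change (13, 57 and 20), and the method should be named there.
2. Keep the printed limits, name the shorter exact method in section 10.4, and replace Clopper-Pearson with it in section 10.6.2.

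The first is simpler because it leaves the committed analysis alone. Neither change affects design, sample size or conduct, so the cost is a text correction.

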In addition, oral tenofovir is being studied for use in prevention of peripartum maternal-to-child transmission of HIV-1 in late pregnancy. Data on the first cohort of 15 women enrolled to Pediatric AIDS Clinical Trials Group (PACTG) Protocol 394 have been presented. Women were given an oral dose of 600 mg of tenofovir either at the onset of labor or four hours before scheduled cesarean delivery, and pharmacokinetics and safety in the mother and infant were evaluated. No significant adverse events in the women or infants were attributed to tenofovir. The maternal tenofovir concentrations were similar to those seen after chronic dosing with 300 mg daily in non-pregnant individuals, despite the dose of 600 mg. Median cord blood levels were 76 ng/mL (range 0-309 ng/mL) and the median cord blood/maternal ratio was 0.69. All levels were below the level of quantitation (25 ng/mL) in the infants at 12, 24, and 36 hours of age. The study is continuing with a dose of 900 mg to the mother at onset of labor or before cesarean delivery. Another study, HPTN 057 is also evaluating maternal intrapartum and neonatal pharmacokinetics and safety of tenofovir. Both of these studies are in preparation for a large Phase III trial (expected sample size of approximately 2000 pregnant women) evaluating the use of oral tenofovir with emtricitabine and nevirapine for prevention of perinatal transmission and development of resistance of HIV-1. This selection is based on the expected effectiveness and safety of oral tenofovir in pregnancy. Given the low levels of tenofovir detected in the cord blood after a maternal oral dose of 600 mg, levels after intravaginal exposure to 40 mg would be expected to be lower, but must be evaluated.

Additional safety data regarding the use of tenofovir in pregnancy are available from the Antiretroviral Pregnancy Registry (APR). Through April 1, 2007, 266 cases of first trimester exposure and 208 cases with exposure to tenofovir later in pregnancy have been reported with no increase in birth defects or unusual pattern of defects detected (first trimester: 7 of 266 (2.6%); later in pregnancy: 3 of 208 (1.4%)).

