HPTN 050 also addressed pharmacokinetics of vaginally administered tenofovir gel. Fourteen of 25 women (56%) with pharmacokinetic results had low, but detectable, serum tenofovir levels (limit of quantitation: 3.0 ng/mL) at some point in the 12 hours after dosing on either Day 0 (following the first dose) or on Day 13 (after daily dosing); three of the 14 had detectable levels on both days. The maximum tenofovir concentrations ( $C_{max}$ ) ranged from 3.0 - 25.8 ng/mL, with no clear dose-concentration relationship identified. For the woman with the 25.8 ng/mL level, this peak level occurred two hours following the dose; the level rapidly declined to 10.9 ng/mL at four hours and was undetectable at 12 hours following the dose. Besides the outlier with the highest tenofovir level, the next highest  $C_{max}$  was 7.1 ng/mL. Considering all women in the PK cohort, the median tenofovir  $C_{max}$  was 3.4 ng/mL (interquartile range: below limit of quantitation [3.0 ng/mL] to 4.7 ng/mL). The median  $C_{max}$  for all subjects (3.4 ng/mL) corresponds to approximately 1% of the maximum ( $C_{max, steady-state (ss)}$ ) and 7% of the minimum (C24 single dose) blood concentrations at steady-state with 300 mg daily oral tenofovir dosing. Findings from CONRAD A04-095 are expected to further inform the pharmacokinetic data on vaginally administered tenofovir gel.

Figure 1 presented below demonstrates tenofovir blood concentration following vaginal administration of tenofovir 1% gel in HPTN 050. All levels for all women with measurable tenofovir levels in the blood are shown. (14 of 25; lower limit of quantitation (LLOQ) approximately 3.0 ng/mL [dotted line]). Legend indicates “cohort” – “ID” – “study day”. For reference the tenofovir level associated with the median 24 hour post-dose blood concentration following an oral 300 mg tenofovir dose is indicated with dashed line.

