### **7.9.2 Network Laboratory**

The Network Laboratory will run the following:

- Urine SDA for chlamydia and gonorrhea
- Trichomonas culture
- Pharmacokinetic analyses (at NL Pharmacology Core)

The following specimens will be collected for pharmacokinetic analyses of tenofovir according to guidelines outlined in the Site SOPs.

- Maternal blood
- Amniotic fluid
- Cord blood
- Placental tissue

- Endometrial tissue

Based on HPTN 050, 64% of measurable samples fell in the 2 to 6 hour sampling window which was the basis for selection of sampling times to maximize capture of peak levels in the blood. Measurable levels were spread almost evenly among the 2, 4, and 6 hour sample times. Subjects' peak tenofovir concentrations occurred throughout this window. In HPTN 050, 38% of measurable levels were after 4 hours so they are somewhat less likely to be measurable, but will be nearly as informative as the 4 hour sample.

MTN-002 will use a more sensitive tenofovir assay than HPTN 050. Our validated liquid chromatography mass spectrometry (LCMS) method has a limit of quantitation (LOQ) of 5 ng/mL, but uses only 50 microliters of fluid. Previous methods have had a LOQ of 3 ng/mL but used 250 microliters. Since assay sensitivity is largely determined by mass in the sample, not concentration, this likely represents a 3 fold improvement in sensitivity if we use a similar volume as in previous studies. To improve even further, we are planning to dedicate 1 mL serum for the blood tenofovir assay to further increase the sensitivity, possibly below 1 ng/mL. This may increase the number of samples quantifiable in the blood assuming similar pharmacokinetics as in HPTN 050.

As stated above, a validated assay for tenofovir in plasma is currently available. Validated assays for tenofovir in endometrial tissue, amniotic fluid and placental tissue have not yet been developed, but are expected to be ready in 2007. Pharmacokinetic samples may be batch shipped from the NL to the NL Pharmacology Core for assay.

The principal parameter of interest after intravaginal dosing will be the AUC. Plasma will also be analyzed for routine pharmacokinetic parameters ( $C_{max}$ ,  $T_{max}$ ).

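### Section 10.4 and the fallback in 10.6.2 judge cord blood by the share of all 16 women with detectable drug, which is only weak evidence on placental transfer unless the assay limit is well below 5 ng/mL

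*Protocol*

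**What the plan says.** Sections 4.2 and 10.2 of the Protocol list placental transfer as a major endpoint, measured by levels in cord blood, placental tissue and amniotic fluid. Section 10.4 works with an absorption rate "defined as the proportion of women with detectable levels of PMPA in plasma, endometrium, cord blood, placental tissue, and/or amniotic fluid". For the sites where little is expected, it states that "16 women would provide 80% power to exclude absorption rate > 25% assuming the true rate of absorption is 5" percent. It adds upper limits from two-sided exact intervals, which "are 20% and 30% if the observed number of absorption in a cohort of 16 women was 0 or 1, respectively".

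Section 10.6.2 is descriptive. If many women are below the limit, it replaces summaries of levels by the proportion detectable with a Clopper-Pearson interval. It also plans ratios of maternal level to time-matched cord, amniotic and endometrial levels.

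On the assay, section 7.9.2 says that the validated plasma method "has a limit of quantitation (LOQ) of 5 ng/mL, but uses only 50 microliters of fluid". It plans to use 1 mL of serum for the blood assay, which might bring the limit under 1 ng/mL. For the other materials, "Validated assays for tenofovir in endometrial tissue, amniotic fluid and placental tissue have not yet been developed".

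**The concern.** A cord blood counts as detectable only if the maternal level at delivery, multiplied by the transfer ratio, reaches the assay limit. Section 10.4 mentions none of these three quantities. When maternal levels are low, cord blood can be below the limit however freely the placenta passes the drug.

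Sections 2.11 and 10.3 expect plasma drug in only about 33% of women, or 0.33 x 16 = 5.3 women. The other 10 or 11 would say nothing about transfer, yet they stay in the denominator. The second hypothesis in 10.3 is framed among women with detectable drug, but the denominator in 10.4 is all 16.

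At stake is the meaning of the likeliest result. With 0/16 or 1/16 cord bloods detectable, a reader could take little transfer from a count that was largely set by the assay limit and the low maternal levels.

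**Working it through.** **Inputs**
- n = 16, true rate 5%, rate to exclude 25% (section 10.4).
- Oral cord/maternal ratio: "the median cord blood/maternal ratio was 0.69" (section 2.4).
- Validated limit: 5 ng/mL on 50 microliters (section 7.9.2).
- HPTN 050 peaks (section 2.10): 25 women, one at 25.8 ng/mL. "Besides the outlier with the highest tenofovir level, the next highest" Cmax was 7.1 ng/mL. The median was 3.4 and the upper quartile 4.7 ng/mL.

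**The protocol's own figures.** With X binomial(16, 0.05), P(X <= 1) = 0.811, which reproduces the stated 80%. P(X = 0) = 0.95^16 = 0.440. The exact two-sided 95% upper bounds are 20.6% at 0/16 and 30.2% at 1/16. So the 80% belongs to at most 1/16, although the interval at 1/16 does not exclude 25%. Only 0/16 does, with power 44%. This mismatch is a separate defect in the same sentence. Both counts are carried below.

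**Maternal level needed.** Limit / ratio = 5 / 0.69 = 7.25 ng/mL. Conversely, cord levels at the HPTN 050 peaks would be:
- median: 3.4 x 0.69 = 2.3 ng/mL
- upper quartile: 4.7 x 0.69 = 3.2 ng/mL
- second highest: 7.1 x 0.69 = 4.9 ng/mL

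Only 1 of 25 women would be detectable, p = 0.04, close to the 5% that section 10.4 assumes.

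**Chance of a low count with transfer at 0.69 in every woman, limit 5 ng/mL**

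| Women high enough | p | P(0/16) = (1-p)^16 | P(at most 1/16) |
|---|---|---|---|
| 1/25 | 0.04 | 0.52 | 0.87 |
| 2/25 | 0.08 | 0.26 | 0.63 |
| 1/50 | 0.02 | 0.72 | 0.96 |

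The 2/25 row counts the woman at 7.1 ng/mL, whose cord level falls just short of 5. The 1/50 row counts the outlier once among at most 50 woman-days. With no transfer, both probabilities are 1.00.

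**Dependence on the limit.** Peaks are assumed log-normal, with delivery at the peak. Fit A has median 3.4 and upper quartile 4.7 ng/mL, so sigma = ln(4.7/3.4)/0.6745 = 0.48. Fit B sets 34% of woman-days above 3 ng/mL and 2% above 7.1. The 34% is (14 + 3)/50, since 14 women were detectable, three of them on both days. Each cell gives p, P(0/16), P(at most 1/16).

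| Cord limit (ng/mL) | Maternal level needed | Fit A | Fit B |
|---|---|---|---|
| 5 | 7.25 | 0.057, 0.39, 0.77 | 0.018, 0.75, 0.97 |
| 3 | 4.35 | 0.30, 0.003, 0.024 | 0.13, 0.10, 0.36 |
| 1 | 1.45 | 0.96, about 0, about 0 | 0.83, about 0, about 0 |

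If the level at delivery is half the peak, P(0/16) is 0.98 to 0.99 at 5 ng/mL and at most 0.001 at 1 ng/mL.

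**The planned ratios.** A cord value below the limit gives no maternal/cord ratio, only a bound: cord/maternal is less than limit/maternal level. At a maternal level of 3.4 and a limit of 5, that bound is 5/3.4 = 1.47, which is uninformative. It drops to 0.69 only at 7.25 ng/mL.

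**The case against.** The strongest case against has several parts, and much of it stands.

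- **No decision rule.** Section 10.4 justifies the sample size and defines its rate as detection. Nothing in the Protocol declares transfer low on the strength of a count. A reader might infer such a rule, but the text does not contain one. The problem is how the result can be read.
- **The assay may be better.** The 5 ng/mL limit is for 50 microliters. On the Protocol's reasoning by mass, 250 microliters gives 5 x 50/250 = 1 ng/mL, and 1 mL is planned for blood. At 1 ng/mL the concern goes away for cord blood. But section 7.9.2 words the lower limit as a plan and a possibility, does not name cord blood, and section 13.3.1 mentions only a single cord aliquot of unstated volume. That silence does not show that cord blood is excluded.
- **Ratios are planned.** They do link cord to maternal levels, and they help in women with both measurable. They have no value when cord blood is below the limit, which is the expected case at 5 ng/mL.
- **Full transfer and no transfer look the same.** This is a tempting reading but too strong: 52% or 87% against 100% is weak discrimination, not none. Nor may the 52% be paired with the 80% power, since they belong to different counts.
- **Thin inputs.** The 4% is one outlier among 25 women, pooled over two gel strengths and two study days. The 0.69 is a median treated as a constant. Section 2.10 expects that late pregnancy may raise absorption, which would raise detection.
- **Other materials.** The ratio 0.69 says nothing about placenta, amniotic fluid or endometrium, and no limit is given for them. The calculation does not extend there.

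**Conclusion.** The point holds, conditionally and for cord blood only. At a 5 ng/mL limit, transfer at the oral ratio would yield about 2% to 8% detectable cord bloods, a range that includes the 5% planned for as very little absorption. The low count would then occur about 52% of the time as 0/16 (26% to 72%), and about 87% as at most 1/16 (63% to 96%). This assumes that HPTN 050 peaks apply at delivery in term pregnancy and that 0.69 represents full transfer. Delivery away from the peak makes it worse; higher absorption in pregnancy makes it better. At 1 ng/mL the low count almost never occurs under full transfer.

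Apart from the limit, women without measurable maternal drug carry no information on transfer, so an all-women proportion bounds fetal-side exposure above the limit, not transfer. The correction is worth making because it is cheap and the interpretation of a major endpoint currently depends on a limit that has not been fixed.

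**What to change.** In sections 10.4 and 10.6.2:

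1. Read a cord blood below the limit as evidence on transfer only in women whose matched maternal level is at least the cord limit divided by 0.69 (7.25 ng/mL at a limit of 5, 1.45 ng/mL at 1). For them, report limit/maternal level as the upper bound of the cord/maternal ratio, and give the number of informative women.
2. Report the all-women figure as the proportion at or above X ng/mL, with X fixed before the samples are assayed, and say that it bounds exposure and not transfer. Do not carry the 0.69 threshold over to placenta, amniotic fluid or endometrium.
3. State that the planned 1 mL low-limit method also applies to cord blood.

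In the same edit, reconcile the 80% power with the interval actually planned.

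The cost is wording and a cord aliquot large enough for the assay, from blood already collected. No participants or procedures are added. The downside is that few women may be informative if the lower limit is not reached: at 5 ng/mL and 1/25, 16 x 0.04 = 0.6 of a woman is expected. At 1 ng/mL and delivery at the peak, 13 to 15 of 16 would be (16 x 0.83 to 16 x 0.96).
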